9.2.2 Study time frame

We will use CPRD GOLD and Aurum EHR data from January 1, 2013 through latest available data (currently March 2019).

- Patient identification period: The patient identification period will be restricted to January 1, 2013 through latest available data as shown in the figure above.
- Cohort entry: CAT diagnosis, hospitalization or emergency department admission or primary care visit with an incident VTE event.
- Index date: The date of first rivaroxaban (or any DOAC) or LMWH use according to registered prescription 7-30 days after CAT event (new-user design).
- Pre-index eligibility period: Patients will be required to have at least 12-months of EHR registration prior to the CAT event.
- Post-index eligibility period: There will be no minimum post-index eligibility requirement for patient identification.
- Follow-up period: There will be a minimum of 3 months and maximum 12-months follow-up period. Patients will be followed from the first recording of AC use (7-30 days after CAT event) until the end of eligibility.

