9.2.3 Selection criteria

To be included in the study patients will have to:

- Be ≥ 18 years of age at the time of anticoagulation initiation
- Have active cancer and acute DVT and/or PE
- Treated with rivaroxaban (or any DOAC) or LMWH as their first recorded anticoagulant prescription 7 to 30 days post-acute CAT event diagnosis
- Have been active in the data set for at least 12-months prior to the index event and had at least one provider visit in the 12-months prior to the acute VTE event

We will exclude patients with:

- Evidence of atrial fibrillation, recent hip/knee replacement (with 90 days of CAT), ongoing VTE treatment, valvular heart disease defined as any rheumatic heart disease, mitral stenosis or mitral valve repair/replacement
- History of inferior vena cava filter before cohort entry
- VKA use between cohort entry and index day (initiation of DOAC or LMWH)
- Evidence of any type of therapeutic anticoagulation use during all available look-back period per written prescription or patient self-report
- Initiation of rivaroxaban or other DOACs or LMWH during the study period at non-therapeutic doses (e.g., enoxaparin at a dose other than 1 mg/kg twice daily or 1.5 mg/kg once daily; dalteparin at a dose other than 200 IU/kg of total body weight)
- Pregnancy
- Recording indicative of palliative care before cohort entry
- Any clinically-relevant bleeding-related hospitalization or VTE recurrence between the initial CAT and the start of observation

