9.3.2 Outcomes definition

The study outcomes will be defined based on Read codes and ICD-9/10-CM diagnosis and procedure codes or laboratory, vital sign and other patient observation results.

Algorithms for the definition of recurrent VTE and of the bleeding events have previously been developed and refined using all information available in CPRD, HES and Office of National Statistics ONS [4, 8].

A random sample of identified potential VTE recurrences and significant bleeding events will be manually reviewed by utilizing patient summaries/profiles including HES APC, HES Outpatient, ONS death registration data (DRD) and PCP recorded symptoms, signs, laboratory tests, diagnostic and therapeutic procedures, medication use, discharge diagnoses, and cause of death to confirm the that outcomes have been appropriately identified.

Primary outcomes

- The risk of recurrent VTE at 3-months
- Composite of any major bleeding or clinically-relevant non-major bleeding-related hospitalization (per the ISTH criteria [9, 10] for identification of bleeding-associated hospitalizations) at 3-months
- All-cause mortality at 3-months

Secondary outcomes

- Recurrent VTE at 6- and 12-months post-index VTE

- Composite of any major or clinically-relevant nonmajor bleeding-related hospitalization at 6- and 12-months post-index VTE, including:
 - Intracranial hemorrhage (ICH)
 - Critical organ bleeding (e.g., intracranial, intraspinal, intraocular, retroperitoneal, intraarticular or pericardial bleeding or intramuscular with compartment syndrome)
 - Extracranial bleeding-related hospitalizations (including trauma-related)
- Composite of any major bleeding or clinically-relevant non-major bleeding-related hospitalization (per the ISTH criteria [9, 10] for identification of bleeding-associated hospitalizations) at 6 and 12-months
- Intracranial hemorrhage (ICH), critical organ bleeding and extracranial bleeding-related hospitalizations as separate outcomes
- All-cause mortality at 6- and 12-months
- Incidence rates of recurrent VTE, any clinically-relevant bleeding-related hospitalization and all cause-mortality in rivaroxaban, DOAC and LMWH patients experiencing CAT regardless of the bleeding risk associated with cancer type
- Duration of anticoagulation treatment and rivaroxaban, DOAC and LMWH discontinuation rates at 3-, 6-, 12-months and all available follow-up

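### The palliative-care exclusion stops at CAT diagnosis, 7-30 days before treatment group and time zero are set, so palliative coding in that gap is neither excluded nor adjusted for and may confound 3-month mortality

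*Protocol*

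**What the plan says.** Section 9.2.2 of the protocol sets two dates. The first is "Cohort entry: CAT diagnosis, hospitalization or emergency department admission or primary care visit with an incident VTE event". The second is the index date: "The date of first rivaroxaban (or any DOAC) or LMWH use according to registered prescription 7-30 days after CAT event". Time at risk begins at the second: "Patients will be followed from the first recording of AC use (7-30 days after CAT event) until the end of eligibility".

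Section 9.2.3 lists the exclusions. The palliative-care criterion is "Recording indicative of palliative care before cohort entry", so it closes at the first date. Two other criteria in the same list cover the gap between the dates: VKA use is screened up to the index day, and patients are also excluded for "Any clinically-relevant bleeding-related hospitalization or VTE recurrence between the initial CAT and the start of observation".

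Section 9.3.3 lists the covariates and has no palliative or end-of-life item. Section 9.7 builds the propensity score from that list and fits a Cox model whose only regressor is the anticoagulant. Section 9.3.2 names "All-cause mortality at 3-months" as a primary outcome.

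**The concern.** Eligibility, baseline and time zero should refer to the same moment. Here the palliative-care criterion is assessed one to four weeks before the moment at which the protocol assigns treatment. A new VTE in a patient with active cancer is an event that can itself prompt a move to palliative care, so codes may well appear in this gap. Such a code can plausibly bear on whether an injection or a tablet is prescribed, and it is strongly related to early death. That makes it a candidate confounder of the mortality comparison.

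No later step removes it. Section 9.7 itself acknowledges that overlap weighting cannot adjust for characteristics left out of the propensity model. The sensitivity analyses in that section do not address this window, and section 9.9 mentions residual confounding only in general terms. Yet palliative status is not unmeasured: the study already has to extract it to apply the exclusion. Death also competes with the other two primary outcomes, recurrent VTE and bleeding, so a distortion in mortality can affect them too.

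**Working it through.** **1. The windows side by side (sections 9.2.2 and 9.2.3)**

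| Item | Assessed up to |
|---|---|
| Palliative-care exclusion | cohort entry (CAT diagnosis) |
| VKA exclusion | index day |
| Bleeding or recurrence exclusion | start of observation |
| Treatment group, index date, time zero | GP prescription, day 7-30 after CAT |

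The palliative criterion leaves a gap of 7-30 days before time zero.

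**2. The protocol's own size figures (section 9.5)**

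Events = 5,600 × 0.6 years × rate. This gives 5,600 × 0.6 × 0.118 = 396 recurrences, × 0.144 = 484 bleeds and × 0.80 = 2,688 deaths, against the stated 390, 480 and 2,670.

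Detectable HR = exp(−(1.960 + 0.842)/√(D·a·(1−a))), where D is the number of events and a the share in one arm; 5% is taken as two-sided. With the stated event counts and 1:1 allocation this gives 0.753, 0.774 and 0.897. At about 37:63 it gives 0.745, 0.767 and 0.894, which round to the stated 0.75, 0.77 and 0.89. The protocol does not give the allocation ratio. The figures reproduce, and 0.89 belongs to deaths within the first year.

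**3. The benchmark that fits the 3-month outcome**

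At 80 deaths per 100 person-years, 3-month mortality is 1 − exp(−0.80 × 0.25) = 0.181. In 5,600 patients that is about 1,015 deaths. At 1:1 the detectable HR is exp(−2.802/√(1,015 × 0.25)) = 0.84.

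**4. Size of the possible bias**

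The true treatment HR is set to 1 with no adjustment through proxies. Spurious HR (DOAC vs LMWH) = ln(1 − risk in DOAC users)/ln(1 − risk in LMWH users), where each 3-month risk is the mixture of palliative and other patients. All shares and palliative mortality figures are assumptions.

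(a) Non-palliative patients die at the protocol's 80 per 100 person-years; palliative patients have 2, 3 or 5 times that hazard.

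| Palliative share, LMWH vs DOAC | ×2 | ×3 | ×5 |
|---|---|---|---|
| 2% vs 1% | 0.99 | 0.98 | 0.97 |
| 5% vs 2% | 0.97 | 0.95 | 0.93 |
| 10% vs 3% | 0.94 | 0.90 | 0.84 |
| 15% vs 5% | 0.92 | 0.86 | 0.80 |
| 5% vs 5% | 1.00 | 1.00 | 1.00 |

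(b) Non-palliative 3-month mortality of 15%; palliative mortality of 50% or 70%.

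- 5% vs 2%, 50%: LMWH 0.05 × 0.50 + 0.95 × 0.15 = 0.1675; DOAC 0.02 × 0.50 + 0.98 × 0.15 = 0.157; HR = ln(0.843)/ln(0.8325) = 0.93.
- 5% vs 3%, 50%: 0.1675 and 0.1605; HR 0.95.
- 10% vs 3%, 70%: 0.205 and 0.1665; HR = ln(0.8335)/ln(0.795) = 0.79.
- 10% vs 2%, 70%: 0.205 and 0.161; HR 0.77.

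Across both sets, the unequal scenarios run from 0.77 to 0.99. Those clearly below 0.84 are 15% vs 5% at five times the hazard, and 10% vs 2-3% at 70% mortality. The 10% vs 3% scenario at five times the hazard (0.844) falls just short of the unrounded benchmark of 0.839.

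(c) Carried to 12 months with constant hazards and equal arms, the 0.93 and 0.79 scenarios give Cox HRs of about 0.96 and 0.89. At the horizon to which 0.89 applies, even the severe one only reaches the line.

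**The case against.** The strongest counter-argument is about timing. Section 9.1 says that patients are routinely discharged with anticoagulant supply whose type and start date are not recorded, and section 9.9 repeats that in-hospital starts are likely to be missed. The GP prescription is therefore a stand-in, and a palliative code on days 0-30 may follow the real drug choice. Excluding on it could condition on a post-treatment event. This stands as a caution and is why the fix includes a sensitivity analysis. It does not remove the mismatch, because the protocol defines new use, baseline and time zero at the index prescription and already screens the same gap for other events.

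The other criteria that cover the gap also have their own reasons: VKA use must be screened to keep the exposure groups clean, and bleeding or recurrence to keep patients outcome-free at time zero. A reader might infer that the protocol contradicts itself. It does not. The windows differ, and the palliative one does not fit the stated time zero.

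The covariate list also helps in part. Besides metastatic disease and cancer type, which are fixed at CAT diagnosis and so miss later decline, it holds cancer treatment within 3 months either side of CAT, days from CAT to first anticoagulant record, frailty (score not specified), hospitalizations, comedications and laboratory values. The arithmetic above assumes none of this adjusts, so for given shares it is an upper bound to the extent that these proxies track palliative status.

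A reader might extend the point to the criterion "History of inferior vena cava filter before cohort entry", which also ends at cohort entry. The documents offer no mechanism or figure tying a filter placed in the gap to a biased comparison, so that is not claimed here.

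**Conclusion.** The point holds as a design weakness worth correcting. The palliative-care cut-off is earlier than the protocol's time zero, and nothing in the covariate list, outcome model or sensitivity analyses captures palliative status recorded in between. Whether this biases 3-month mortality, and in which direction, depends on unequal coding between arms, which the protocol does not quantify. Under the assumed shares, all placing more palliative patients on LMWH, the spurious HR lies between about 0.77 and 0.99; with equal shares it is 1.00.

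It is tempting to set these values against 0.89 and conclude that this gap alone can create or cancel a significant mortality result. The documents do not support that as a general statement. The 0.89 rests on about 2,670 first-year deaths in the whole DOAC and LMWH cohort. At 3 months the matching figure is about 0.84, and only the severe scenarios pass it. For rivaroxaban vs LMWH after removal of cancers with high bleeding risk, deaths are fewer and the detectable HR lies further from 1.

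**What to change.** In section 9.2.3, apply the palliative-care exclusion to records on or before the index date. Report, by arm, how many patients this removes between CAT and index; that count shows directly whether the imbalance exists. Because some patients may have started anticoagulation in hospital without a record, add a sensitivity analysis that keeps the present cut-off at cohort entry and enters palliative coding up to the index date as a propensity score covariate. Agreement between the two analyses would settle the matter; disagreement should be reported beside the mortality result.

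No new data source is needed, since the codes are already extracted for the exclusion. The cost is a slightly smaller cohort, by a number that cannot be computed from the protocol, and one extra analysis. The IVC-filter criterion can stay as it is.

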9.2.4 Representativeness

The CPRD primary care dataset is one of the largest databases of longitudinal medical records from primary care in the world. Patients included in CPRD GOLD and Aurum are broadly representative of the UK general population in terms of age, sex and ethnicity. The CPRD is very widely used internationally for epidemiological research.

9.3 Variables

9.3.1 Exposure definition

Newly-initiated on rivaroxaban (or any DOAC) or LMWH per recorded written prescription on day 7-30 post-acute CAT event diagnosis. Patient self-report of medication use, over-the-counter medications are not registered in UK CPRD data. On-treatment analysis will be performed in the UK- CPRD databases. The vast majority of written prescriptions are filled in primary care in the UK with instructions, and we will be able to define patterns of treatment (stopping, continuous, switching, reinitiating, etc.).

Analysis at 3-, 6 and 12-months will be performed to assess the potential impact of the early anticoagulation discontinuation.

9.3.2 Outcomes definition

The study outcomes will be defined based on Read codes and ICD-9/10-CM diagnosis and procedure codes or laboratory, vital sign and other patient observation results.

Algorithms for the definition of recurrent VTE and of the bleeding events have previously been developed and refined using all information available in CPRD, HES and Office of National Statistics ONS [4, 8].

A random sample of identified potential VTE recurrences and significant bleeding events will be manually reviewed by utilizing patient summaries/profiles including HES APC, HES Outpatient, ONS death registration data (DRD) and PCP recorded symptoms, signs, laboratory tests, diagnostic and therapeutic procedures, medication use, discharge diagnoses, and cause of death to confirm the that outcomes have been appropriately identified.

Primary outcomes

- The risk of recurrent VTE at 3-months
- Composite of any major bleeding or clinically-relevant non-major bleeding-related hospitalization (per the ISTH criteria [9, 10] for identification of bleeding-associated hospitalizations) at 3-months
- All-cause mortality at 3-months

Secondary outcomes

- Recurrent VTE at 6- and 12-months post-index VTE

- Composite of any major or clinically-relevant nonmajor bleeding-related hospitalization at 6- and 12-months post-index VTE, including:
 - Intracranial hemorrhage (ICH)
 - Critical organ bleeding (e.g., intracranial, intraspinal, intraocular, retroperitoneal, intraarticular or pericardial bleeding or intramuscular with compartment syndrome)
 - Extracranial bleeding-related hospitalizations (including trauma-related)
- Composite of any major bleeding or clinically-relevant non-major bleeding-related hospitalization (per the ISTH criteria [9, 10] for identification of bleeding-associated hospitalizations) at 6 and 12-months
- Intracranial hemorrhage (ICH), critical organ bleeding and extracranial bleeding-related hospitalizations as separate outcomes
- All-cause mortality at 6- and 12-months
- Incidence rates of recurrent VTE, any clinically-relevant bleeding-related hospitalization and all cause-mortality in rivaroxaban, DOAC and LMWH patients experiencing CAT regardless of the bleeding risk associated with cancer type
- Duration of anticoagulation treatment and rivaroxaban, DOAC and LMWH discontinuation rates at 3-, 6-, 12-months and all available follow-up

9.3.3 Covariate definition

Patient baseline characteristics such as age, gender, comorbidities, cancer-specific data and comedications will be collected at the index date or from the last recorded value within the baseline period. The presence of characteristics will be assessed from patients' medical and pharmacy data in the baseline period (see Annex 1).

Demographic characteristics

- Sex
- Age
- Race
- Individual DOAC or LMWH used to treat CAT
- Number of days between CAT and first recording of anticoagulation use

Clinical characteristics

- Presence of the following clinical characteristics will be assessed from patients' medical and pharmacy data in the baseline period:
 - **Comorbidities/prior history/risk scores:**
 - Number of days from January 1, 2013 to qualifying CAT diagnosis
 - Cancer type(s) present at CAT diagnosis
 - Metastatic disease at time of CAT diagnosis
 - Active/recent treatment (within 3-months pre- or post-CAT diagnosis)
 - Chemotherapy/immunotherapy
 - Radiation therapy
 - Surgical
 - Initial anticoagulation therapy on day of CAT diagnosis
 - Intracranial bleeding
 - Systemic embolism
 - Deep vein thrombosis
 - Pulmonary embolism
 - Heart failure
 - Hypertension
 - Ischemic stroke/transient ischemic attack
 - Peripheral vascular disease
 - Myocardial infarction
 - Percutaneous coronary intervention
 - Coronary artery bypass grafting
 - Any major bleed

- Major adverse limb events (need for surgical or endovascular revascularization or limb amputation)
- Gastrointestinal bleeding
- Central venous catheter
- Liver disease
- Coagulopathy
- Gastroesophageal reflux disease/heartburn
- Anemia
- Asthma
- Chronic obstructive pulmonary disease
- Sleep apnea
- Smoker
- Alcohol abuse
- Anxiety
- Depression
- Lower extremity paralysis
- Psychosis
- Osteoarthritis
- Diverticulitis
- Crohn's disease or ulcerative colitis
- Active or treated *Helicobacter pylori*
- Hypothyroidism
- Recent major surgery within 12 weeks of index event
- Dementia
- Recent trauma (with 90-days)

- Primary hypercoagulable state (e.g., activated protein C resistance, prothrombin gene mutation, antiphospholipid syndrome, lupus anticoagulant syndrome and other primary thrombophilia (per Read code; ICD-9 or -10 coding provided in Annex 1))
- Prior history of VTE
- Varicose veins
- Chronic venous insufficiency (per Read code or ICD-9 /-10 coding provided in Annex 1)
- Acute coronary syndrome
- Carotid stenosis
- Pneumonia
- Osteoporosis
- Orthopedic surgery
- Rheumatoid arthritis/collagen vascular disease
- Proteinuria
- Ischemic (coronary) heart disease
- Number of hospitalizations for any cause during the baseline period
- Vascular disease (defined as myocardial infarction, peripheral artery disease or aortic plaque)
- Frailty (per specific Frailty Score)
- **Comedications**
 - Aspirin
 - P2Y12 Inhibitors
 - Other antiplatelet agents
 - NSAIDs
 - COX-2-specific NSAIDs
 - ACE inhibitors or ARBs

- β -blockers
- Diltiazem
- Verapamil
- Dihydropyridine calcium channel blockers
- Loop diuretic
- Thiazide diuretic
- Digoxin
- Amiodarone
- Dronedarone
- Other antiarrhythmic drugs
- Statins
- Other cholesterol lowering drugs
- Metformin
- Sulfonylureas or glinides
- Thiazolidinediones
- Dipeptidyl peptidase-4 inhibitors
- Glucagon-like peptide-1 agonists
- Insulin
- Benzodiazepines
- SSRIs or SNRIs
- Other antidepressants
- Proton pump inhibitors
- Histamine-2 receptor antagonists
- Systemic corticosteroids
- Exogenous estrogen therapies

- Strong CYP3A4 inhibitors (e.g., protease inhibitors, -azole antifungals)
- Strong CYP3A4 inducers (e.g., phenytoin, carbamazepine, rifampin, St. John's wort)
- Chemotherapy agents (various)
- Laboratory values and vital signs at baseline
 - SBP
 - DBP
 - Hemoglobin
 - D-Dimer
 - Serum creatinine
 - Reported eGFR
 - Height
 - Weight
 - Body mass index (BMI)
 - Platelet count

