9.1 Study design

[figure not shown]
We will perform a retrospective cohort analysis using CPRD GOLD and Aurum HES-linked datasets, from January 2013 through latest available data. Patient identification and flow is depicted in **Figure 1**.

Adults diagnosed with active (primary or metastatic) cancer experiencing a hospitalization or emergency department admission or a primary care visit with an incident VTE, being administered rivaroxaban or other DOACs or a LMWH will be included. CPRD and their linked databases do not include information on in-hospital medication use. Patient discharge with anticoagulation supply is routine practice. However, neither the type of AC use, the date of medication start nor the amount of supply are recorded in CPRD or linked databases. Therefore, the first AC recording by the GP, between day 7 and day 30 after index date, will be used to define the type and duration of AC use and to allocate patients with acute VTE to the respective exposure, i.e. DOAC or LMWH. The 7-30 days window has been selected based on previous studies in this population [2, 4]. Subjects will need to be registered with their primary care practitioner (PCP) for at least 12-months prior to the acute CAT event.

Active cancer in this study will be defined as cancer being actively treated, diagnosed within 6-months prior of the index CAT or associated with metastatic disease (regardless of time from initial cancer diagnosis). We will exclude patients with an indication for OAC use to treat other conditions (i.e. atrial fibrillation, prophylaxis after hip/knee replacement in the last three months, stable coronary or peripheral artery disease, long-term VTE prophylaxis) or use of OAC during the 12-months prior to the CAT.

Figure 1: Schematic of VTE analysis

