9.7 Data analysis

Baseline characteristics will be analyzed using descriptive statistics. Categorical data will be reported as percentages and continuous data as medians with accompanying 25%, 75% ranges or means \pm standard deviations (SDs). Descriptive analysis will be performed for each of the three distinct cancer cohorts listed above, namely, (1) the cohort of cancer patients without gastrointestinal and genitourinary cancers, (2) the cohort defined by the ISTH CAT guidelines (in acute CAT patients without a malignant neoplasm associated with a high risk of bleeding) and (3) an all cancer type cohort.

To adjust for potential confounding between the rivaroxaban (or DOAC) and LMWH cohorts, propensity scores will be calculated using a multivariable logistic regression model. The propensity score model will include commonly used variables and accepted risk factors for differential anticoagulation exposure identified at baseline including demographics, comorbidities, laboratory values, vital signs, other clinical observations and outpatient medication use (prescription and over-the-counter). All clinical characteristics listed in section 9.3.3 of this protocol will be included in the propensity score model. Propensity scores will then be used to assign weight to individual patients in the analysis using an overlap weighting approach. Overlap weighting assigns weights to patients that are proportional to their probability of belonging to the opposite treatment cohort. By design, overlap weighting results in the exact balance of all variables included in the propensity score model. This method of adjustment retains all patients in the dataset (unlike propensity score matching) and gives less weight to patients with extreme propensity scores (which is often a concern with inverse probability weighting).

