Propensity scores will be estimated based upon commonly used variables and accepted risk factors for differential anticoagulation exposure identified during the baseline period including demographics, comorbidities, laboratory and vital signs and concurrent outpatient co-medication use. All clinical characteristics listed in section 9.3.3 of this protocol will be included in the propensity score model. Given the retrospective nature of the data analysis, the presence of a comorbid disease diagnosis will be identified based upon the recording of the specific comorbid read codes. Missing data for covariates will occur when an existing co-morbidity or co-medication is not recorded in the database. In such case we will assume that the respective patient did not suffer from the respective co-morbidity/did not use the respective co-

Reference Number: RD-SOP-1214
Supplement Version: 7

medication. Information on time varying variables e.g. BMI and smoking status will assumed to be constant unless a different variable entry is recorded. Whenever meaningful, missing data will be presented in separate categories labelled "not stated" or "unknown". No imputation will be performed for potentially missing outcomes/endpoint data. Separate propensity score models will be fit once for the primary analysis and for each subgroup analysis.

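### Sections 9.3.3 and 9.7 put into the propensity score an initial-treatment variable that the data cannot supply for hospital-diagnosed patients and, read literally, the study drug itself

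*Protocol*

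**What the plan says.** Protocol section 9.7 states that "propensity scores will be calculated using a multivariable logistic regression model". It names the inputs as factors "identified at baseline including demographics, comorbidities, laboratory values, vital signs, other clinical observations" and medication use, and it says twice: "All clinical characteristics listed in section 9.3.3 of this protocol will be included in the propensity score model".

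Two entries in section 9.3.3 matter here:

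- Under demographic characteristics: "Individual DOAC or LMWH used to treat CAT".
- Under clinical characteristics: "Initial anticoagulation therapy on day of CAT diagnosis".

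No entry in section 9.3.3 is marked as descriptive only.

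On what the data hold, section 9.1 says that in-hospital drug use is absent from CPRD and its linkages. Of the supply given at discharge it says that "neither the type of AC use, the date of medication start nor the amount of supply are recorded in CPRD or linked databases". For that reason exposure is taken from the GP record on days 7 to 30.

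Section 9.7 also lists as a model input "other clinical observations and outpatient medication use (prescription and over-the-counter", while section 9.3.1 says that "over-the-counter medications are not registered in UK CPRD data".

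**The concern.** The propensity score carries the whole adjustment for confounding. Section 9.7 enters only the anticoagulant received into the Cox model, on the assumption that the score has balanced everything else. An input that cannot be measured, or that is the exposure itself, therefore has no second line of defence.

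The two main items fail in different ways. The initial-therapy item fails quietly. The model runs, and overlap weighting balances the mean of whatever code was entered, so a reader of the balance table may believe that the arms were alike in first treatment. The individual-agent item fails openly: it predicts the arm perfectly and leaves no usable score.

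**Working it through.** No figure in the plan depends on this point apart from the weight formula in section 9.7, so the check is a comparison of sections followed by a short calculation.

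**1. Initial anticoagulation on the day of CAT.** It is listed as a clinical characteristic, so the rule on all clinical characteristics captures it directly. What can be known about it depends on the route of entry:

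| Route of entry | What the data hold for day 0 | Resulting code |
|---|---|---|
| Hospital or A&E | Drug not recorded (9.1); the HES content described in 9.4 includes no medication | Not used, or unknown |
| GP, prescription on day 0 | Recorded, but 9.2.3 wants the first recorded anticoagulant on days 7 to 30 | Excluded if first is read strictly; observed if it means first within the window |
| GP, no prescription on day 0 | Nothing recorded | Not used |

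The missing-data text in section 9.7 gives two possible codes. Unrecorded comorbidities and comedications count as absent, and a separate unknown category is allowed where meaningful. Either way:

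- Under the strict reading, no included patient has an observed day-0 drug, so the item carries no information on therapy.
- Under the looser reading, an observed drug occurs only in GP-diagnosed patients, so the item largely marks place of diagnosis.

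**2. Individual agent.** It is listed under demographics, which section 9.7 names as inputs. The agent determines the arm in both comparisons (rivaroxaban versus LMWH, and all DOACs versus LMWH).

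Overlap weight = 1 − PS for treated patients and PS for LMWH patients.

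- Treated: PS → 1, so the weight → 1 − 1 = 0.
- LMWH: PS → 0, so the weight → 0.

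Illustration: the abstract expects at least 1,000 rivaroxaban users and at least three times as many LMWH users, hence 1,000 + 3 × 1,000 = 4,000 simulated patients, of whom 1,035 fell in the treated arm. Four ordinary covariates with assumed coefficients were used, and the logistic model was fitted by Newton-Raphson.

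| Model | Iterations | Largest weight | Sum of weights |
|---|---|---|---|
| Without agent | 5 to 25 (converged) | 0.935 | 728.4 per arm |
| With agent | 5 | 2.0e-3 | 8.10 |
| With agent | 10 | 1.4e-5 | 0.0545 |
| With agent | 20 | 6.2e-10 | 2.5e-6 |
| With agent | 25 | 4.2e-12 | 1.7e-8 |

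Without the agent, the effective sample size, (Σw)²/Σw², is about 2,911 of 4,000. With it, the weights are not only tiny but equal. At 5 iterations the mean weight is 8.10/4,000 = 2.0e-3, the same as the largest, and the effective sample size is 4,000. Equal weights mean that an analysis run on them would be unadjusted. Matching within a calliper would fail as well, because no LMWH patient has a score near that of a treated patient. The assumed coefficients affect the illustration but not the limit.

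**3. Over-the-counter use.** Section 9.7 names it as an input and section 9.3.1 says that CPRD does not register it. Section 9.3.3 lists no such variable, so only the phrase itself is affected.

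**The case against.** **Individual agent.** It sits under the demographic heading, whereas the binding sentence speaks of clinical characteristics. It enters only through the general word demographics, in a sentence about recognised predictors of which anticoagulant is given, and the study drug is the exposure rather than a predictor of it. Separation would show at the first fit. This stands in part. A reader might infer that the primary analysis will end with zero weights. The documents do not support that: zero is a limit under a literal reading, and the likelier outcome is that the analyst drops the variable. That would still be an unplanned change to the main confounding model.

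**Initial therapy.** The absent-if-unrecorded rule is written for comorbidities and comedications, and an unknown category is permitted. A reader might infer that every hospital patient is miscoded, but this is not established: a patient coded unknown is not miscoded, nor is one who truly had no anticoagulant that day. The protocol also gives no split by place of diagnosis from which to size the problem. A constant would drop out of the model harmlessly, and a proxy for place of diagnosis has some use. Section 9.7 plans a sensitivity analysis limited to patients admitted for the event, and section 9.9 concedes missed in-hospital starts and unmeasured factors in general.

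These points limit the harm without resolving the contradiction. Restricting to admitted patients makes place of diagnosis more uniform but leaves first treatment unobserved. Section 9.9 treats missed in-hospital starts as exposure misclassification, expected to be non-differential, and not as a confounder that the model claims to include.

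**Over-the-counter use.** The parallel sentence later in section 9.7 omits the phrase, and section 7 says that the protocol is based on the US one. It may simply be carried-over wording.

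**Conclusion.** The point holds as a specification error that should be corrected before the propensity model is fitted.

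- **Initial therapy** is the more important item, because its failure is silent. The protocol requires it in the model and also says that it is not available for hospital-treated patients. How many patients this affects cannot be sized from the documents. The conclusion rests only on section 9.1 and on the rule that all clinical characteristics enter the model.
- **Individual agent** gives degenerate weights in both comparisons if read literally. This rests on taking demographics to mean the demographic list in section 9.3.3. The practical risk is an undocumented correction at the analysis stage rather than a biased result that goes unnoticed.
- **Over-the-counter use** is a genuine but minor contradiction.

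The documents do not show that the planned analysis must collapse or that its results would be wrong by a stated amount.

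**What to change.** In section 9.7, replace the general reference to section 9.3.3 with an explicit list of propensity-score inputs, and:

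1. Mark the individual DOAC or LMWH as descriptive only and exclude it from the score.
2. Remove initial anticoagulation on the day of CAT from the score. Add place of CAT diagnosis (HES APC, A&E or primary care), which the entry routes in section 9.2.2 and the linkages requested in section 9.4 provide. It does not measure first treatment and should not be described as doing so.
3. Delete over-the-counter use as an input.
4. In section 9.9, name unmeasured initial therapy and over-the-counter aspirin and NSAID use as residual confounders.

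The cost is protocol wording and one derived variable. No further data or linkage is needed, and the study size is unaffected.
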